### **Sample Size Analysis**

At each stage of randomization, the combination of tailored messaging factors follows a resolution 5 fractional factorial design. A sample size of 1,000 patients is sufficient to detect inferiority at a margin of 0.075 with 80% power. We note that performing this sample size calculation is non-standard as it requires estimating the best tailoring message, which requires optimizing over a potentially large number of potential tailored message combinations; we corrected for these multiple comparisons by inverting a projection interval. However, we plan to follow patients for a total of two years. Assuming 33% attrition over this time period, an initial sample of 1,500 is sufficient.

Primary endpoints include compliance with screening recommendations (measured via MMR) as well as potential mediators of intervention effectiveness (such as exposure to the intervention, psychological processing of content, and self-reported communication with a healthcare provider about screening).

Secondary endpoints including cancer detection rates as well as long-term behavioral changes (i.e. whether patients request screening the following year). They will be analyzed as descriptive statistics without anticipated power calculations.

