## **6. Study Design**

We will evaluate the VHT intervention using a fractional factorial experimental design embedded within a sequential, multiple assignment, randomized trial (SMART). The fractional-factorial design allows estimation of the optimal tailored message assuming only lower-order interactions and requires far fewer samples. For example, a full factorial design of 10 factors at two levels would involve runs of size 4,096 whereas a fractional factorial design that does not confound any pairwise interactions would involve runs of size 79. In short, the fractional factorial experimental design allows us to go beyond simply testing the efficacy of tailored vs. non-tailored messages by honing in on the specific elements of a message that are most salient to the patient.

We will also collect longitudinal data on outcomes associated with exposure to the intervention (Phase 3). Participants in the treatment arms who have completed their initial screening within the first 12 months of the study will receive an email invitation one year after the intervention. This message will invite them to view a booster of the intervention consisting of another message encouraging repeated screening. Compliance will be assessed via self-reporting and MRR for all patients as well as through tracking in MyUFHealth.

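### The 80% power at a margin of 0.075 is tied to estimating the best message but matches only a single uncorrected half-versus-half contrast; under the implied pairwise model, best-message power is far lower

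*Combined protocol and SAP*

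**What the plan says.** Section 6, Sample Size Analysis, gives the plan's only power statement: "A sample size of 1,000 patients is sufficient to detect inferiority at a margin of 0.075 with 80% power". It calls the calculation non-standard because "it requires estimating the best tailoring message, which requires optimizing over a potentially large number of potential tailored message combinations", and says that these multiple comparisons were handled by inverting a projection interval. Allowing for 33% attrition, it arrives at 1,500 enrolled.

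On the design, the same subsection says that at each randomization stage "the combination of tailored messaging factors follows a resolution 5 fractional factorial design". The opening of Section 6 says the design "allows estimation of the optimal tailored message assuming only lower-order interactions", and describes "a fractional factorial design that does not confound any pairwise interactions" as needing 79 runs.

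The plan does not state alpha, sidedness, expected compliance, the scale of the margin, what the best message is compared with, which model is fitted, or the projection critical value.

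**The concern.** A resolution 5 design is chosen so that every main effect and every pairwise interaction can be estimated. A predicted value for one message then sums many estimated coefficients, and its error is much larger than that of a comparison between two halves of the sample. Searching over messages and correcting for the search widens the interval again. An 80% figure at 0.075 with 1,000 patients looks too good for that task and about right for a much simpler one.

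The enrolment of 1,500 rests on this figure. If it is read as covering message optimisation, a claim that one message is best, or lies within 0.075 of the best, would rest on intervals much wider than the margin.

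**Working it through.** **Inputs from the plan.** N = 1,000 evaluable; margin 0.075; power 80%; resolution 5 design; pairwise interactions unconfounded; projection correction (all Section 6). The outcome is screening compliance, which is binary (Section 5).

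**Assumed, because not stated.** The margin is a risk difference. Overall compliance p is 10-50%, with variance s² = p(1-p). The test is two-sided 5% (z = 1.96) or one-sided 5% (z = 1.645). There are 10 two-level factors, varied to 12 below.

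**1. The plan's own figure.** It cannot be recomputed from the stated inputs. A plain 500-versus-500 contrast has variance 4s²/N. For 80% power its standard error must be 0.075/(1.96 + 0.842) = 0.0268, so s² = 0.0268² × 1,000/4 ≈ 0.179, which is p of about 23%. At one-sided 5%, 0.075/(1.645 + 0.842) = 0.0302 gives s² ≈ 0.227, or p of about 35%. So 1,000 patients fit a single contrast chosen in advance, with no search and no correction. The attrition step is consistent: 1,000/0.67 = 1,493.

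**2. Factor count.** Section 6 says "a full factorial design of 10 factors at two levels would involve runs of size 4,096". Ten factors give 2^10 = 1,024, and a pairwise model of 1 + 10 + 45 = 56 coefficients. The printed values fit 12 factors: 2^12 = 4,096 and 1 + 12 + 66 = 79.

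**3. Variance of a two-message contrast under the pairwise model.** With ±1 coding in an orthogonal design, each coefficient has variance s²/N. If two messages differ in d of k factors, d main effects and d(k-d) pairwise terms change sign, each contributing 4s²/N:

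variance = 4 × d(k+1-d) × s²/N, against 4s²/N for half versus half.

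- k = 10: the ratio d(11-d) is 10 at d = 1 or 10, and 30 at d = 5 or 6. All 1,023 contrasts from one message in a constructed 128-run resolution 5 design agree.
- k = 12: the ratio runs from 12 to 42.
- Best message against the average of all messages, k = 10: 55s²/N, a ratio of 13.75.

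**4. Power at 0.075, N = 1,000, before any correction.** Power = Φ(0.075/SE - z). At ratio 10, SE = √(40 p(1-p)/1,000).

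| Compliance | SE | Two-sided 5% | One-sided 5% |
|---|---|---|---|
| 10% | 0.060 | 23.9% | 34.6% |
| 20% | 0.080 | 15.3% | 24.0% |
| 30% | 0.092 | 12.7% | 20.4% |
| 50% | 0.100 | 11.3% | 18.5% |

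These use the smallest two-message variance for 10 factors. At ratio 30, two-sided power is 6-11% over the same rates. At ratio 12 (12 factors) it is 10-21%. Simulation at N = 1,000 and ratio 10 gave 16%, 13% and 10% at 20%, 30% and 50% compliance, two-sided.

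At ratio 10, 80% power would need overall compliance of about 1.8% or less (2.3% if one-sided), or the mirror image near 100%. At 20-50% compliance it would need roughly 7,000 to 14,000 patients across the two alpha choices.

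**5. Effect of a correction.** The plan's critical value is unknown. A Scheffé-type projection on 55 degrees of freedom has a critical value of about 8.6. At p = 50%, 0.075/0.100 = 0.75 against 8.6 gives power of essentially zero. Even a Bonferroni correction for only ten comparisons (critical value 2.81) gives 2-3% at 20-50% compliance.

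**6. What 1,000 patients do support.** For one full-sample arm or factor contrast, two-sided 5%, the difference detectable with 80% power is 2.80 × 2 × √(p(1-p)/1,000) = 0.071, 0.081 and 0.087 at 20%, 30% and 40% compliance.

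**The case against.** The strongest reply is that the estimand above is inferred. The plan says that the calculation involves estimating the best message, but not that the 0.075 test contrasts two messages, nor which model is fitted. The Background frames the hypothesis as virtual human versus text-only, an arm-level comparison that can reach 80% with 1,000. Alpha and compliance are open too: at 5% compliance, power at ratio 10 rises to 41% (two-sided) or 53% (one-sided). With fewer than 10 factors the minimum ratio falls.

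All of this stands, and it makes the power figures conditional. It does not rescue the stated 80%. The arm-level reading requires neither a best message nor a projection correction, yet the plan says that its calculation involved both.

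A reader might also infer that no difference of 0.075 between two messages can be detected. The documents do not support that. If only main effects are fitted, two messages differing in one factor differ by that main effect (ratio 1), and uncorrected power is 84% at 20% compliance. With two factors differing it is 55% at 20% compliance and 80% at 10%; with five differing, 19-26% at 20-40% compliance. For the best message against the average of all messages under main effects only (ratio 2.5), power is 32-71% two-sided at 10-50% compliance. Under one-sided 5% it reaches 80% only at about 10% compliance, still before correction.

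**Conclusion.** The concern holds in conditional form. The 80% figure cannot be reproduced from the plan. It coincides with a single pre-chosen, uncorrected half-versus-half contrast at an unstated compliance of about 23% (35% if one-sided 5%), which is not the calculation the plan describes. If the figure refers to a two-message contrast under the main-effects-plus-pairwise model, uncorrected power at 0.075 is at most about 11-24% (two-sided 5%) or 18-35% (one-sided 5%). Those ranges assume 10 factors, 10-50% compliance and a risk-difference margin. Any projection correction lowers them.

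It would go too far to quote 11-24% as the trial's power, or to call the figure a proven arithmetic slip: the inputs that would settle either point are not in the documents. The variance ratio of at least 10 is exact for 10 factors under the pairwise model. With the 12 factors that 4,096 and 79 imply it is at least 12, so resolving the factor count upward strengthens the point.

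**What to change.** Rewrite the power statement in the Sample Size Analysis:

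- Apply 80% only to a named single full-sample arm or factor contrast, with its assumed compliance and alpha. At two-sided 5% the detectable difference is about 0.071, 0.081 or 0.087 at 20%, 30% or 40% compliance.
- State that the trial does not have 80% power at 0.075 for best-message comparisons under the pairwise model with the projection correction. Limit the sentence to that model, since a main-effects analysis behaves differently.
- Specify the fitted model, the comparator for the best message and the projection critical value. Report the best message's compliance with its corrected interval as estimation, not as a powered margin test.
- Reconcile the factor count in Section 6: 10 factors as written, or the 12 that 4,096 and 79 imply.

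The cost is SAP wording and a less favourable stated figure. No more patients are needed.

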## **7. Data Management:**

We worked with representatives of UF Health Network and MyUFHealth to situate the intervention within MyUFHealth. The interaction itself will be hosted using Virtual People Factory (VPF), a web platform which hosts virtual human interactions. We will use Amazon Web Service (AWS) to store data from the interaction as well as host the virtual human webpage. For our design, human subjects need to be randomized to see either a demographically-matched VH or a demographically-dissimilar VH. They will also see either a video recruiting message a UF Health provider or a written recruiting message with a photo of the provider.

Representatives from IDR will set up weekly pulls of eligible patients and will upload lists of these patients and their contact information onto a secure, password-protected server housed in the University of Florida's Health Sciences Center. Each human subject will be sent a message in MyUFHealth inviting them to click on a link. We will use script to append the subject's MyUFHealth ID number to the end of the link to create a customized URL. For patients initially recruited outside of MyUFHealth through UF Qualtrics, after entering name, patient ID, email, and demographics a unique ID will be created and appended to a customized URL link. Clicking on the URL takes the subject to the secure server housed in the University of Florida's Health Sciences Center. The secure server runs a program replacing the MyUFHealth ID number with a random Participant ID number before redirecting the subject to the virtual human app. The program records both numbers in a key document which is updated daily and uploaded to the secure, password-protected server.

In this way, no PHI leaves the secure UF Health network, but we can still record the subjects' interactions within the intervention and match their answers up with the survey data collected from MyChart. The participant ID number on its own contains no PHI. The only way the random participant ID number on its own could be used to identify human subject and access PHI would be to breach the security of the UF Health Sciences Center server and MyUFHealth. No PHI leaves the UF system. No PHI is transmitted to VPF or AWS. All data will be monitored systematically to identify any security weaknesses, and data files will be backed up to protect against data corruption.

After completing the intervention, participants will be redirected to Qualtrics, an online survey hosting site, to complete the post-test questionnaire. Their random Participant ID will be appended to their Qualtrics questionnaire, allowing us to link their responses to their actions in the intervention. Qualtrics data will be backed up regularly and stored in the secure, password-protected UF Health IT server.

Study staff will participate in community health fairs and events where study information will be presented and interested patients will have the ability to speak with our study staff to receive details on how to participate in the study. Consistent with study procedures, all participants receive a unique participant ID that prevents researchers to link participant data. The mapping between the actual patient ID and generated unique ID is only known to the research coordinator, COE director, and Assistant Director of Clinical Community Navigation in order to provide FIT test results (received or not; positive or negative screen). Other members of the research team will not be aware of the actual patient ID. This process ensures that study data is de-identified and PHI will be protected.

Data monitoring will be conducted by the Data Safety Management Committee (DSMC), consisting of [name] (PI), and [name] (Co-I). The DSMC will meet as needed to discuss the safety and integrity of the

data and will submit annual reports to the University's SMRC (Scientific Review and Monitoring Committee).

### **Data Retention Policy and Data Sharing**

Data will be collected and retained in accordance with HIPPA requirements and standard procedures. Data about eligibility, recruitment, and patient progress through the study will be stored in a secure REDCap database that only the research coordinators, postdoc, and other necessary staff can access. We will store only the minimum amount of data required to determine patient eligibility for enrollment in the trial and the postdoc will regularly review all data for quality control and compliance.

We will retain data on EMRs reviewed in Epic for the duration of the trial and for as long as is required by law. Retained data will be provided to authorized medical providers at UF Health Family Medicine and UF Health Internal Medicine upon request to assist them in updating patient medical records and documenting discrepancies in CRC screening status.

We will share data associated with the trial with outside investigators by depositing these data in Azkaban, a file sharing system approved by UF Integrated Risk Management. Data include participant responses to survey questions and information about participant interactions with the intervention, demographic data (including participant zip code), as well as select medical information such as screening status for CRC. Data will be deidentified where possible and data will only be stored on SharePoint for the duration of analysis, after which they will be removed from the system.

Data will be shared with investigators working at other accredited universities for the purposes of analysis. The names and Institutions of persons either given or denied access to the data, and the bases for such decisions, will be recorded. Participants will acquire IRB approval from their home institution to review data.

### **8. Possible Discomforts and Risks:**

We anticipate that this study is deemed to be minimal risk. This study poses minimal risk to participants because it involves no medical treatment and the intervention itself consists of information that would be given to a participant in the course of a normal visit with his or her doctor. There is some psychological risk to participants who are not familiar with the technology, as they may become frustrated. However, we have developed the app in conjunction with potential users to ensure that it is as user-friendly and navigable as possible. The questionnaire does not contain any items that are likely to cause emotional distress. There is no social risk, as the participants will not be physically seen by the researchers. We have enacted all necessary technical protections to keep data safe and data will be de-identified.

Patients will be provided with a phone number to contact study staff. In the unlikely event that a patient wishes to not be contacted again, they will be removed from the study immediately and will stop receiving messages through MyChart as it pertains to the study.

#### Protections for “Break-the-Glass” Patients

The Epic EMR system has special protections in place for particularly sensitive medical documents or files, such as HIV status and information as well as data on specific psychiatric conditions. These documents or files are protected from view by a “Break-the-Glass” lock which, when opened, triggers a privacy audit. During the chart review process, it is possible that coordinators and other study staff may encounter Break-the-Glass documents or files, indicating a patient with special status.

We have enacted special safety procedures for this patient population to ensure their privacy while minimizing the risk of excluding them unnecessarily from recruitment and furthering disparities. First, research staff have been trained to immediately close the document or file and avoid proceeding if they encounter a Break-the-Glass warning. If the patient is enrolled in C2S, coordinators will continue reviewing the record to the best of their ability to establish eligibility without viewing any Break-the-Glass documents or files. If they cannot determine eligibility status, the patient will be exited from the study. If the patient is deemed eligible, they will be enrolled in the trial as normal. Patients who are not enrolled in C2S will be immediately exited upon discovery of a Break-the-Glass warning.

Second, patients with Break-the-Glass warnings will be deemed a special cohort within the framework of the clinical trial and subject to additional checks to ensure patient well-being. The DSMB, along with the clinic co-investigators, will review the records and participation rates of Break-the-Glass patients quarterly and will make decisions about continuing to enroll such patients.

### **Adverse Event Reporting**

If any team member encounters or becomes aware of an adverse event, they should notify the PI and Postdoc within 5 business days. The PI and Postdoc will confer and inform the co-investigators, project officer, and University of Florida IRB about the event as appropriate. All team members have been made aware that they should inform the PI and Postdoc if they encounter an adverse event. Potential, but unlikely adverse events include participants talking to other participants about their study condition or misperceiving the intervention as a reduction in their healthcare services (e.g., virtual appointment instead of face-to-face appointment). The intervention team will discuss each adverse event and determine if changes to the protocol are necessary.

### **9. Possible Benefits:**

**Public Health Impact:** The proposed study improves public health by contributing to research on how to best deliver effective screening messages to minority and rural patients. A primary goal of Healthy People 2020 is to increase the percentage of individuals screened for CRC across population subgroups to 80%. The proposed study will reduce health disparities and associated morbidity and mortality due to CRC by increasing FIT screening among minority and rural populations through a novel, culturally sensitive intervention. By leveraging existing infrastructure within the health system (i.e., clinical data warehouse), we will create a cost-effective communication strategy for delivering personalized screening messages to diverse patient populations.

### **10. Conflict of Interest:**

There are no real or potential conflicts of interest in regards to this research project for any members of the study team.
